TMS is a non-invasive neuromodulation strategy that has shown some benefit in WC patients. TMS involves a short intense current in a coil applied over the scalp to generate a magnetic field which then passes through the skull and induces an electric field that, depending on frequency of stimulation can depolarize or hyperpolarize local cortical neurons(24,25). A key feature of the current proposal is that I will improve upon previous applications of TMS in dystonia by targeting the deep brain region of striatum, as opposed to superficial cortex; and do so in a way that may be sufficient to induce long-term synaptic plasticity responses. I hypothesize that focal TMS stimulation designed to induce LTD in WC dystonia will improve decreased striatal activity on fMRI. To test this hypothesis, I will dose TMS using knowledge of brain circuitry in dystonia. A key parameter for effective dosing of TMS is the specific brain region to target. The striatum is a deep brain tract that is not directly targetable by TMS. However, stimulating cortical regions with TMS in a manner that affects projection neurons (as opposed to intra-cortical circuits) provides access to striatum.

Fortunately, in dystonia and WC, much work has been done to define relevant cortical inputs to striatum (25–34).

Prior research demonstrates 2 cortical regions that can be targeted by TMS to affect striatal activity in WC subjects. One potential cortical target is premotor cortex. In primates, radioactive tracer injected at premotor and motor cortex demonstrated direct projection of premotor cortical axons to striatum, particularly putamen(35,36). Studies in WC using *in vivo* tract tracing suggest the premotor to putamen pathway is impaired(37).

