Visit 2: 70 FHD subjects and 70 HV from visit 1 will be recruited to undergo a functional MRI brain at Duke BIAC. To assess patient's baseline, subjects will copy a sentence using their dystonic **left or right hand** in fMRI suite alternated by periods of rest using an MRI compatible digital tablet. Writing task and control motor task will be back-projected onto a screen located at the head of the MRI bed using an LCD projector. Subjects will view the screen via a mirror system located in the head coil. Task onset will be electronically synchronized with the MRI acquisition computer using Cigal computer software. Task administration and collection of writing data will be computer controlled. The scanning session will take about 1.5 hr and include structural MRI, DTI, Swan, resting state fMRI and task-based fMRI.

BOLD images will be acquired using a GE Premier Performance 3T MRI scanner, which is an improved version of GE's FDA-approved Premier system, but with better capabilities for high-resolution imaging. All operational parameters on this improved system will be within FDA guidelines to meet the same minimal risk device criteria and ensure safety of human subjects. As such, an Investigational Device Exemption (IDE) is not necessary. The research conducted under this protocol is not to evaluate the safety and efficacy of this device.

A urine drug screen and pregnancy test prior to visits 3-5.

Visits 3, 4 and 5: 5 healthy volunteers who completed visits 1 and 2 will be recruited to undergo development of TMS stimulation protocol at Duke BSRC. Following protocol development, 20 focal hand dystonia subjects who completed visits 1 and 2 will also be recruited to undergo TMS stimulation at Duke BSRC. All 25 subjects will undergo the procedure as detailed below:

[figure not shown]

Figure 3: Sequence of events for research visits 3, 4, and 5. A) Overview of TMS stimulation, writing assessment and fMRI imaging. B) TMS session will be divided into 4 blocks of writing, each 5 minutes.

1. MRI Brain images from visit 2 will be uploaded to a neuro-navigation system (Brainsight: Rogue Research, Montreal, Canada) at the Brain Stimulation Service Stimulation Service Center

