fMRI data: All image pre-processing will be implemented using the FSL program (<https://wiki.biac.duke.edu/biac:fsl>). Block design fMRI data will be extracted by time-series modeling using rectangular time windows for the motor task and rest periods. Group data will then be analyzed using GLM modeling. Any fMRI network identified in writing performance from previous fMRI research using the writing task in dystonia patients will be prospectively applied to the fMRI data of the subjects. Specifically, the imaging data from the pre and post fMRI sessions will be log transformed and subtracted from each other at each site in each subject. The global mean across sites will be subtracted from each log-transformed regional value, producing regional values normalized to each subject's global mean activity. In a second normalization, the mean for each site across subjects will be subtracted from each regional value. The result of these two normalizations is a subject x region matrix with the mean activity within and across subjects removed. This will be cross-correlated with the patterns previously found in order to quantify pattern expression for individual subjects in the present group. These individual subject pattern expressions will be entered into regressions predicting brain performance in order to verify that the patterns predict performance in new group. In addition, pattern expression will be used to predict rTMS effects on writing task performance (for example, differences in RT with active and sham rTMS).

Data & Safety Monitoring

- Summarize safety concerns, and describe the methods to monitor research subjects and their data to ensure their safety, including who will monitor the data, and the frequency of such monitoring. If a data monitoring committee will be used, describe its operation, including stopping rules and frequency of review, and if it is independent of the sponsor (per 45 CFR 46.111(a) (6)).

Safety monitoring: The subjects will be fully informed of the nature of the study requirements prior to enrollment and periodically throughout the study. The subject's well being will be continuously monitored by the experimenter, and the

Principal Investigator will report all serious adverse events in an expedited manner to the Duke University Health System (DUHS) Institutional Review Board (IRB) office and all applicable regulatory authorities in accordance with the Center's standard operating procedures.

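### The fMRI pattern score logs an unnamed quantity: a task-minus-rest estimate has no log at or below zero, and logged signal intensity does not isolate writing-related change

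*Combined protocol and SAP*

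**What the plan says.** The fMRI paragraph of Data Analysis & Statistical Considerations sets out this sequence.

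- Extraction: "Block design fMRI data will be extracted by time-series modeling using rectangular time windows for the motor task and rest periods".
- Transformation: "the imaging data from the pre and post fMRI sessions will be log transformed and subtracted from each other at each site in each subject".
- First centring: "The global mean across sites will be subtracted from each log-transformed regional value, producing regional values normalized to each subject's global mean activity".
- Second centring: "the mean for each site across subjects will be subtracted from each regional value".
- Output: "The result of these two normalizations is a subject x region matrix with the mean activity within and across subjects removed".

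The matrix is then correlated with activity patterns from earlier work. The resulting score per subject goes into regressions on performance and is used to predict the effect of rTMS on writing.

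On acquisition, the visit 2 description in Design & Procedures says that "BOLD images will be acquired using a GE Premier Performance 3T MRI scanner" and that subjects copy a sentence "in fMRI suite alternated by periods of rest using an MRI compatible digital tablet". The sample size paragraph names fMRI as an outcome measure for the 20 TMS patients.

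The plan does not say whether the logged quantity is a task-minus-rest estimate, a percent change or a mean signal. It gives no offset, floor, exclusion or missing-value rule for values at or below zero.

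**The concern.** A block-design model with task and rest windows ordinarily yields a task-minus-rest effect for each region. That effect is signed: noise or deactivation can put it at or below zero, where a log cannot be taken. The other obvious candidate, mean signal intensity, is positive and can be logged, but its log contains no comparison with rest.

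The score is meant to express a writing network and to predict the rTMS effect on writing. On the first reading some entries of the subject-by-region matrix do not exist, and an analyst would have to choose a shift constant or an exclusion after seeing the data. The Data Storage and Management principles ask for the statistical approach to be fixed in advance and clearly stated, so this choice should not be left open. On the second reading the score can be computed but mixes writing-related change with change in resting signal.

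**Working it through.** The plan states no figure on this point: no regional mean or SD, no number of regions, no expected share of non-positive values. There is nothing to reproduce. The check takes the two readings in turn. From the plan: 20 TMS patients and the order of the steps. All other inputs are assumptions.

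**Reading A: the logged value is a task-minus-rest estimate.** Assume it is normal across subjects with mean/SD = d.

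- Share of single values at or below zero = Φ(−d).
- A subject-region cell needs both sessions positive. Share of cells lost = 1 − P(pre > 0 and post > 0), from a bivariate normal with equal means and pre-post correlation 0.5 (assumed).

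| d | Single values ≤ 0 | Cells lost | Of 20 patients, one region |
|---|---|---|---|
| 0.5 | 31% | 45% | 9.1 |
| 1 | 16% | 25% | 5.1 |
| 2 | 2.3% | 4.1% | 0.8 |
| 3 | 0.1% | 0.3% | 0.1 |

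At d = 1 the cell loss is 29% with pre-post correlation 0 and 22% with 0.8, so d matters far more than the correlation.

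Correlating a subject with a pattern uses all its regions. For an assumed five-region pattern, with regions and sessions independent, patients with a complete row = 20 × Φ(d)^10: 0.5 at d = 0.5, 3.6 at d = 1 and 16 at d = 2. With assumed correlations of 0.5 between regions and 0.7 between sessions, simulation gives about 4.5, 9 and 17, and about 20 at d = 3.

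The loss is selective by construction, since a cell is lost only if a value is at or below zero.

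**Reading B: the logged value is mean signal in the task window.** Signal intensity is positive, so every log exists. Write the pre-post log difference for subject i and region r as a(i,r) + b(i,r) + ln c(i), where a is the writing-related change, b the change in the region's resting signal, and c a scale factor common to all regions.

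- Subtracting the subject's mean over regions removes ln c(i).
- Subtracting each region's mean over subjects removes any part of b that is the same for all subjects in that region.
- The part of b that differs by region and by subject stays, in the same units as a.

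An illustration with invented signal values, before centring:

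| Case | Pre rest | Pre task | Post rest | Post task | ln(post task / pre task) | Change in ln(task / rest) |
|---|---|---|---|---|---|---|
| Baseline shift only | 1000 | 1020 | 1020 | 1040.4 | 0.0198 | 0.0198 − 0.0198 = 0 |
| Writing effect rises | 1000 | 1020 | 1000 | 1040.4 | 0.0198 | 0.0396 − 0.0198 = 0.0198 |

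Logged task signal cannot tell the two cases apart. The within-session log ratio can, and it is close to percent signal change: a 2% rise gives ln(1.02) = 0.0198.

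**The case against.** The strongest reply is that the plan never says a task-versus-rest estimate is logged. It refers only to imaging data, and its next step, subtracting a global mean of logs, is ratio scaling, which makes sense for positive values. On that reading no cell is lost, the difference of logs has no units, and a session-wide scale factor cancels. All of that stands. It does not answer the narrower criticism that no rest condition is removed. A log(task/rest) measure would meet both problems, and the text does not rule it out, but it does not specify it either.

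Three stronger inferences are tempting, and the documents do not support them.

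- That many values would be lost. No mean/SD ratio is given. Over d from 0.5 to 3 and the correlations tried, complete five-region rows run from about 0.5 to 20 of 20 patients. The number of regions and the rule that one missing region removes a patient are also assumptions.
- That baseline putamen activity would be overstated. The Background section does say "I hypothesize that focal TMS stimulation designed to induce LTD in WC dystonia will improve decreased striatal activity on fMRI", but nothing shows that this hypothesis is tested through the logged score. The paragraph mentions group GLM modeling separately and names no regions in the network.
- That dropping low values inflates the score by a calculable factor. The mean of a truncated variable on the raw scale is not what is analysed. The score is a log difference centred twice, which removes mean level. Selective loss could still distort it, but by an amount not derived here.

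It is also fair to say that the TMS work is called a pilot and that visits 3 to 5 are directed at safety and feasibility. That limits the weight of the point, not its correctness.

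**Conclusion.** The concern holds in conditional form. The transformation as written leaves the logged quantity unnamed, and each of the two obvious candidates gives a faulty score. A task-minus-rest estimate makes the score undefined for an unknown share of cells, selectively the low-activity ones, with no rule for handling them. Mean signal intensity makes it computable but not specific to writing.

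The size under the first reading rests wholly on an assumed normal distribution and mean/SD ratio, and ranges from serious to negligible. Under the second nothing is lost; the size of the contamination depends on how far regional resting signal drifts between sessions, which the plan does not give. No sample-size figure in the plan depends on this point. It is worth correcting before analysis because a concrete replacement is available at almost no cost.

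**What to change.** Replace the log-and-subtract sentence with one that names the quantity: for each site and subject, compute the within-session task-versus-rest effect, either as percent signal change or as log(task signal / rest signal), and take its post-minus-pre difference with no further log. Then apply the two normalizations and the pattern correlation as written. Choose the log(task/rest) form if the earlier patterns were built on log data; the documents do not show whether they were.

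Percent signal change may be negative without difficulty, and the log ratio is defined whenever both signals are positive, so no rule for non-positive effects is needed.

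The cost is one sentence of analysis text and no new data. Scores may be on a slightly different scale from those published for the earlier patterns; correlation with the patterns is still possible.

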Official Title: Development of Mechanistically Informed Therapy for Task-Specific Dystonia Using Noninvasive Neuromodulation

Protocol#: Pro00094131

NCT#: NCT06422104

Document Date: 11/09/2023 (Version 1.31)

General Information

*Please enter the full title of your protocol:

Development of Mechanistically informed Therapy for Task-Specific Dystonia Using Noninvasive Neuromodulation

*Please enter the Short Title you would like to use to reference the study:

Neuromodulation Therapy for Task-Specific Dystonia

* This field allows you to enter an abbreviated version of the Study Title to quickly identify this study.

Standard Research Summary

Purpose of the Study

- Objectives & hypotheses to be tested

The overarching goal of this study is to develop a non-invasive neurostimulation therapy for patients with focal hand dystonia (FHD). Specifically, the data obtained from this study will determine if engaging the striatum during non-invasive brain stimulation in the form of Transmagnetic Stimulation (TMS) can provide prolonged improvement of dystonic symptoms. Previous work in this field has advanced our understanding of regional brain circuit disruptions in dystonia and shown some efficacy in improving focal dystonia using non-invasive brain stimulation, though as of yet the effects are relatively modest and not enduring.

Goal: To characterize baseline behavioral and structural differences between focal hand dystonia subjects and healthy volunteers and evaluate safety and feasibility of neurostimulation therapy.

Visit 1: 70 FHD subjects and 70 healthy volunteers (HV) will be recruited to provide writing samples on digital writing tablet at Duke Brain Stimulation Research Center (BSRC).

Visit 2: A small cohort of 70 FHD subjects and 70 HV from visit 1 will be recruited to undergo functional MRI brain at Duke Brain Imaging and Analysis Center (BIAC). Data from visit 2 will also be used to localize the cortical target for TMS stimulation in visits 3, 4 and 5. Overall, data from visits 1 and 2 will be used to establish baseline outcome measures for visits 3, 4 and 5.

A urine drug screen and pregnancy test prior to visits 3-5.

[figure not shown]
[figure not shown]

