Visit 3, 4 and 5: 5 HV who completed visits 1 and 2 will be recruited to undergo development of TMS stimulation protocol at Duke BSRC. TMS Stimulation will be provided up to 20 minutes (at 10Hz) with a writing sample during stimulation. Subjects will also perform a writing assessment before and after each stimulation block. An fMRI will be performed after completion of each TMS stimulation session.

20 focal hand dystonia subjects who completed visits 1 and 2 will also be recruited to undergo 3 visits of TMS stimulation at Duke Brain Stimulation Center. The 3 visits will each be 1 week apart. 2 visits will involve active TMS and 1 visit will be sham TMS. During one of the active TMS visits, TMS coil will be applied to the premotor cortex for brain stimulation while during the other active TMS visit, TMS coil will be applied to the primary sensory cortex. TMS stimulation protocol will consist of 10Hz stimulation for up to 20 minutes with a writing task during the stimulation block. Subjects will undergo a writing assessment before and after each stimulation block and complete TMS side effects survey. Writing task is different from writing assessment in that writing task will only be used as part of the investigational therapy while writing assessment will be data collected for outcomes measures. fMRI will be performed after completion of each of the 3 TMS visits.

Background & Significance

- Should support the scientific aims of the research

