 3. Healthy volunteers will undergo TMS stimulation protocol development. Subjects will receive 10Hz active stimulation at premotor cortex during one visit and primary sensory cortex during another visit for up to 20 minutes with stimulation intensity up to 120% of resting motor threshold which is within the published safety guidelines (47) and based on previously published protocol used in multiple human studies(13–16). The resting motor threshold is a baseline stimulation intensity determined using the protocol in step 2. Additional stimulation parameters including duration of continuous stimulation, interstimulus interval, stimulation intensity, orientation of magnetic coil, biphasic or monophasic stimulation will be developed with healthy volunteers based on the published safety guidelines(47), writing assessment (includes writing and non-writing sampling) and feasibility within 20 minutes stimulation paradigm.
 4. WC subjects will undergo TMS stimulation visits 3, 4 and 5. 2 visits will include active TMS stimulation while the remaining one visit will be a control sham stimulation. Of the 2 active TMS stimulation visits, subjects will receive TMS at premotor cortex during one visit and at primary sensory cortex during the other active TMS visit. The dosage of active stimulation will be 10Hz for up to 20 minutes with resting motor threshold up to 120% which is within the published safety guidelines (47) and based on previously published protocol used in multiple human studies(13–16). During both active and sham stimulation blocks, subjects will be asked to perform a writing task of writing a diverse paragraph as an online stimulation task. The stimulation block will be preceded and followed by a writing assessment and TMS acute side effects survey to assess safety of the stimulation. Visit 3, 4, and 5 will occur 1 week apart. Subject will undergo fMRI after each of the 3 TMS visits.

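### The fMRI plan measures change from a pre-stimulation scan that can only be Visit 2 and names no active-minus-sham imaging contrast, so its stated steps cannot estimate the TMS effect on striatal activity

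*Combined protocol and SAP*

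**What the plan says.** Under Data Analysis & Statistical Considerations, the fMRI data paragraph states that "imaging data from the pre and post fMRI sessions will be log transformed and subtracted from each other", site by site within each subject. It does not say which session is the pre session. Two normalisations follow: each subject's global mean over sites is removed, then each site's mean over subjects. The resulting matrix is correlated with known patterns, and the pattern scores enter regressions that predict performance.

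The scan schedule appears in three places:

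- Purpose of the Study, patients: "fMRI will be performed after completion of each of the 3 TMS visits".
- Purpose of the Study, healthy volunteers: "An fMRI will be performed after completion of each TMS stimulation session".
- Design & Procedures, step 4: "Subject will undergo fMRI after each of the 3 TMS visits".

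The same step lists what surrounds stimulation on the day: "The stimulation block will be preceded and followed by a writing assessment and TMS acute side effects survey". A scan is not among these. On the baseline, Purpose of the Study says that "data from visits 1 and 2 will be used to establish baseline outcome measures for visits 3, 4 and 5", and the Visit 2 description in Design & Procedures also presents that scan as the baseline.

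Each patient has three TMS visits a week apart: one premotor, one primary sensory and one sham. The Analysis and Statistics paragraph makes sham versus active a factor for the handwriting outcomes only. The fMRI paragraph mentions active and sham once, as an example of a behavioural difference that pattern scores might predict.

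**The concern.** A pre/post difference isolates a stimulation effect only if little else changes between the two scans. Here the pre scan is a separate visit. The gap from Visit 2 to the first TMS visit is not given, and later TMS visits are one or two weeks further away. Each change score can therefore contain elapsed time, scanner variation, familiarity with the scanner and practice at the writing task.

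Background & Significance makes two imaging questions central: whether TMS improves reduced striatal activity on fMRI, and which of the two cortical targets better modulates the putamen. The sample size paragraph names fMRI as an outcome measure. If the stated steps cannot answer these questions, the imaging contrast will be chosen after the data are seen, although the data management principles ask for the statistical approach to be set in advance and clearly stated.

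**Working it through.** The plan gives no figure to reproduce. The check is to trace the scans, write out the change score, and follow it through the stated steps.

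**1. Candidates for the pre scan.** Visit 2 comes before all TMS. For the second and third TMS visits the previous week's scan is also earlier, but it follows active or sham stimulation. The text describes no other scan, so Visit 2 is the only TMS-free choice.

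**2. The change score on the log scale.** For patient *i* under condition *c* at TMS visit *k* = 0, 1, 2:

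- Visit 2 scan: *u_i* + error
- Post scan: *u_i* + *s* + *d*·*k* + *τ_c* + error
- Change from Visit 2: *s* + *d*·*k* + *τ_c* + error
- Active minus sham: (*τ_A* − *τ_S*) + *d*·(*k_A* − *k_S*) + error

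Here *s* is the shift shared by all post scans, *d* the weekly drift and *τ* the stimulation effect. Visit 2 and *s* both cancel in the last line. The contrast is therefore the same whether built from post scans or from changes from Visit 2.

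**3. Illustration.** The documents give no effect sizes, so these are assumptions: *τ_A* = 0.05, *τ_S* = 0, *d* = 0.

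| Shared shift *s* | Active change | Sham change | Active minus sham |
|---|---|---|---|
| 0 | 0.05 | 0.00 | 0.05 |
| −0.05 | 0.00 | −0.05 | 0.05 |
| −0.10 | −0.05 | −0.10 | 0.05 |
| +0.05 | 0.10 | 0.05 | 0.05 |

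The bias in the active change equals *s*. A simulation with 20 patients agreed with the table to within about 0.003.

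**4. Visit order.** Assume a weekly drift *d* = −0.02.

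- Sham always last, premotor first: 0.05 + (−0.02)(0 − 2) = 0.09.
- Sham always first, premotor second: 0.05 + (−0.02)(1 − 0) = 0.03.
- Order as evenly spread as 20 patients allow: 0.045 to 0.050 in simulation.

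The plan states no order. Twenty patients cannot be split equally over the six possible orders (20/6 = 3.33), so a visit term is useful even with near balance. That term can be estimated only if order differs between patients.

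**5. Centring across subjects.** If each site's mean is taken over the subjects in one session, the centred change is (change_i − mean change), and its average is zero by construction. Both *s* + *d*·*k* and the mean *τ_c* disappear. The simulation gave a mean of 0.000 in every scenario. What remains is differences between patients, which can serve the pattern regressions but carries no information on the average TMS effect.

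**The case against.** The best defence has four parts.

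- **Visit 2 is the declared baseline.** This stands. What is missing is a definition of pre in the fMRI paragraph; using Visit 2 to describe baseline is not a fault.
- **The normalisations remove drift.** A reader might infer that session effects will be reported as TMS effects, or that false positives will be inflated. The documents do not support that. They name no test of mean change from Visit 2; the global-mean step removes a whole-brain shift, and centring within a session removes a drift common to patients. But centring removes the average TMS effect too, so this defence leaves the plan without an estimate of it.
- **Group data go into a general linear model, which could include active versus sham.** It could: the plan does not exclude the contrast. But it states no factors or contrasts for imaging, while it does state them for handwriting.
- **This is a pilot, and Visits 3 to 5 are described as serving safety and feasibility.** That limits the weight of the point. It does not remove the stated striatal hypothesis or the comparison of targets.

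A reader might also infer that the design itself cannot answer the question for lack of a same-day scan before stimulation. It can, because the sham scans are already scheduled. Figure 3, which gives the sequence of events, is not shown in the available text, so a scan drawn only there cannot be ruled out.

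**Conclusion.** The point holds as a defect of the stated analysis. Change from Visit 2 alone mixes the stimulation effect with time, repeat-scan and practice effects. The later centring, if done within a session, removes that mixture and the mean TMS effect together. No imaging contrast of active with sham is written down. As written, the steps cannot show whether TMS changes striatal activity or which target does so better.

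The size cannot be given from the documents; the values above are illustrations. The conclusion rests on the text's schedule being complete and on centring within a session, which the description of a subject-by-region matrix suggests but does not settle. Centring pooled over the three sessions would keep differences between sessions, but the contrast would still be unnamed. The algebra leaves out carry-over between weekly visits. The correction should be made before the imaging data are analysed; it is not an obstacle to running the study.

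**What to change.** Rewrite the fMRI data paragraph to:

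1. Define the pre session as Visit 2 and use it for baseline description.
2. For the patients, define the TMS imaging effect as the within-patient post-active minus post-sham difference (equivalently the difference in change from Visit 2), separately for the premotor and primary sensory targets.
3. Include visit number in the model.
4. Estimate this effect before any centring across subjects, and keep the centred matrix for the pattern-expression regressions only.
5. State that the order of the three visits is balanced or randomised. With one fixed order, visit and condition cannot be separated.
6. Say that the contrast does not apply to the 5 healthy volunteers, for whom active stimulation at two sites is described but no sham.

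The cost is a rewritten paragraph and slightly more analysis. No scans or visits are added.

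### The regression meant to verify published fMRI writing patterns is specified only on pre/post change maps (at most 25 people) with an undefined outcome, and the up to 140 baseline task scans are not used for it

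*Combined protocol and SAP*

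**What the plan says.** The method is in the fMRI paragraph of Data Analysis & Statistical Considerations. Networks linked to writing in earlier fMRI work in dystonia patients are to be applied prospectively to this study's data. The only imaging input described is a difference: "the imaging data from the pre and post fMRI sessions will be log transformed and subtracted from each other at each site in each subject". That matrix is normalised twice, first by each subject's global mean and then by each site's mean across subjects, and cross-correlated with the published patterns. The resulting scores are "entered into regressions predicting brain performance in order to verify that the patterns predict performance in new group". A further sentence adds a second use: "In addition, pattern expression will be used to predict rTMS effects on writing task performance".

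Design & Procedures settles who can supply a difference map. For Visits 3 to 5, "5 healthy volunteers who completed visits 1 and 2 will be recruited to undergo development of TMS stimulation protocol" and "20 focal hand dystonia subjects who completed visits 1 and 2 will also be recruited to undergo TMS stimulation at Duke BSRC". It then states: "All 25 subjects will undergo the procedure as detailed below". A scan follows each of the three TMS visits. The only scan described before any stimulation is at Visit 2.

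For that baseline, "Visit 2: 70 FHD subjects and 70 HV from visit 1 will be recruited to undergo a functional MRI brain at Duke BIAC". The session includes task-based fMRI while copying a sentence, and writing data are collected in the scanner. Participants may opt out of Visit 2.

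**The concern.** Two things do not fit the stated aim of verification.

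First, the quantity. A network derived from writing performance describes activity while a person writes. Subtracting the pre scan from the post scan removes the stable part of that activity, and the second normalisation removes the average change at each site. What remains is how individuals differ in change after a stimulation visit. If the outcome is how well someone writes, the regression would not test whether the published pattern replicates. The plan calls the outcome brain performance and does not say whether it is a level or a change, which task it comes from, or which of the three post scans supplies the map.

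Second, the sample. Verifying a writing pattern needs no stimulation, yet the specification confines it to people who had stimulation. The better-matched and larger data set, the Visit 2 task scans with simultaneous writing data, is already in the design.

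At stake is whether the study can say anything useful about the patterns in a new group. A null result from 25 change maps would be hard to interpret, and a positive one might not mean replication.

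**Working it through.** **Inputs.** From Design & Procedures: 20 + 5 = 25 people with post-stimulation scans, and 70 + 70 = 140 planned baseline scans. The plan gives no sample size, effect size or power for this regression, so there is no figure to reproduce. Assumed here: two-sided alpha 0.05, one predictor, and a true correlation r of 0.3 to 0.4, with 0.5 shown for range.

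**Power.** By Fisher's z, power = Φ(atanh(r)·√(n−3) − 1.96), the opposite tail being negligible. The correlation detectable with 80% power is tanh((1.96 + 0.84)/√(n−3)).

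Example at n=25, r=0.3: atanh(0.3) = 0.3095; √22 = 4.690; product 1.452; 1.452 − 1.96 = −0.508; Φ = 31%.

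| Sample | n | r=0.3 | r=0.4 | r=0.5 | Detectable r |
|---|---|---|---|---|---|
| Change maps, patients only | 20 | 25% | 42% | 62% | 0.591 |
| Change maps, all TMS participants | 25 | 31% | 51% | 73% | 0.535 |
| Baseline, patients, illustrative shortfall | 48 | 55% | 81% | n/a | 0.395 |
| Baseline, patients as planned | 70 | 72% | 93% | 99% | 0.330 |
| Baseline, everyone as planned | 140 | 95% | >99% | >99% | 0.235 |

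The n=48 row is 70 × (1 − 0.31) = 48.3. The 31% is the protocol's screening failure rate, not a Visit 2 attrition rate, so this row only illustrates a shortfall. A group term in the baseline regression costs one degree of freedom, which is negligible at these sizes.

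**Crediting all three post scans.** 25 × 3 = 75 maps. With an assumed within-person correlation of 0.5, the effective n is 75/(1 + 2 × 0.5) = 37.5. Power is then 44%, 70% and 90% at r = 0.3, 0.4 and 0.5. This helps, but stays below 70 patients at baseline.

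**Precision.** The 95% interval is tanh(atanh(r) ± 1.96/√(n−3)). For an observed r of 0.3 it runs from −0.11 to 0.62 at n=25, and from 0.14 to 0.44 at n=140.

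**Change against level.** Suppose baseline performance correlates r with baseline expression and relates to post expression only through it. Let pre and post expression have equal variance and correlate ρ. The correlation of (post − pre) with baseline performance is then (rρ − r)/√(2 − 2ρ). With r = 0.5:

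- ρ = 0.3 gives −0.30 and 30% power at n=25.
- ρ = 0.7 gives −0.19 and 15% power at n=25.

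The same pattern tested on level would have r = 0.5 and 73% power at n=25. If performance correlated equally with both scans, the numerator would be zero and the change map would carry no information on it. These figures illustrate the mismatch and apply only if the outcome is a level.

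**The case against.** The fair case against has four parts.

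- **The baseline scans are not idle.** A reader might infer that 140 scans go unused. The documents do not support that. The purpose section uses Visit 2 to localise the stimulation target and Visits 1 and 2 to set baseline outcome measures, and the group GLM is not restricted to TMS participants. Only this verification omits them.
- **The rTMS analysis does not hang on verification.** It is tempting to read the check as a step that must succeed before the patterns are applied to rTMS effects. The text introduces the second use as an addition, with no order, gate or pass criterion.
- **The outcome might be a change.** If it is, change regressed on change is coherent. This cannot be excluded. A level is the more natural reading because rTMS effects are listed separately, but that is inference. What is certain is that the outcome is undefined.
- **This is a pilot, and r is assumed.** The sample-size section says so of the fMRI and TMS work, and no decision rests on this regression. One cannot say that a valid pattern would usually fail at n=25: that holds only for true correlations below about 0.4, and power is 73% at 0.5. The patterns also come from dystonia patients, so patients alone are arguably the closest replication set, and there the gain is smaller.

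These points limit the claim but do not remove it. Pilot status explains a small stimulation sample. It does not explain confining a check that needs no stimulation to that sample. The protocol's own data-management principles also ask for the statistical approach to be fixed in advance and clearly stated.

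**Conclusion.** The point holds in a limited form. As written, the verification regression can draw on at most 25 people, uses change maps, and has an undefined outcome. No check of the patterns on the better-matched Visit 2 task scans is planned.

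For true correlations of 0.3 to 0.4, moving the check to baseline raises power from about 31–51% (44–70% if all three post scans are credited at a within-person correlation of 0.5) to 72–93% with 70 patients, or 95% to over 99% with all 140. With a shortfall to 48 patients it would be 55–81%. The correlations, alpha and achieved Visit 2 numbers are assumptions.

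That a change map is the wrong quantity is conditional on a level outcome. This weakens a secondary, exploratory analysis that is cheap to improve; it does not threaten the safety and feasibility aims of Visits 3 to 5.

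**What to change.** In the fMRI paragraph of the analysis section:

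1. Define the performance outcome: which writing measure, from which task, and whether level or change.
2. Run the verification on Visit 2. Compute pattern expression from the baseline task maps of everyone scanned, and regress Visit 2 in-scanner writing performance on it with a term for patient or volunteer, so that the group difference alone cannot create the association. Report patients alone as well, and the number actually scanned.
3. Keep the change maps for the rTMS questions. State which post scan is used for each comparison or, if all three are used, how repeated scans per person are modelled.
4. Do not make the rTMS analysis conditional on the verification result. The plan sets no such condition, and none is needed.

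If the sponsor prefers to confine verification to TMS participants, the plan should say why. The cost is a few sentences and a modest extra analysis of scans already planned, with no new data and no added participant burden.
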